1.2 Trial registration

- ClinicalTrials.gov identifier: NCT04389333

1.3 Protocol version

- Version 1.0 published on Feb 3rd, 2020.

2.1 Introduction and rationale

COVID-19, a respiratory disease that spreads via direct contact or through droplet transmission, has caused a major disruption in the healthcare system since it was first identified in 2019 [1]. Endoscopic procedures during the pandemic were divided into urgent endoscopy, semi-urgent endoscopy, and elective endoscopy, with the aim of preventing infection among healthcare professionals and providing necessary medical services [2]. For patients who required urgent gastroscopy, the face-to-face contact with endoscopists, aggressive suctioning, and coughing [3] during examination brought opportunities for transmission. Considering the reduced endoscopy volume in most endoscopy departments, diagnosis of patients who needed semi-urgent endoscopy and elective endoscopy may have been delayed [4]. Therefore, focusing on how to return to gradually return to provision of routine endoscopy services while maintaining safety for endoscopists deserves attention [5]. Capsule endoscopy provides a great view of the gastrointestinal tract through use of a miniature, pill-sized camera and it is as accurate as other gastrointestinal endoscopy modalities [6]. Its unique advantages include single use, excellent tolerance, and minimal medical staff requirement, which reduces the risk of exposure to pathogenic microorganisms and cross-infection [7] and makes it an appropriate method for examining and triaging an endoscopy department during the COVID-19 pandemic [8]. However, capsule endoscopy cannot be used to avoid face-to-face contact between endoscopists and patients who have asymptomatic COVID-19 cases [9]. Herein, we describe a novel noncontact magnetically controlled capsule endoscopy (ncMCE) system using a remote control system to separate endoscopists and patients physically, which was developed and tested in our medical center [10,11]. The objective of the present study was to evaluate the feasibility and safety of ncMCE for gastric examination.

2.2 Study design

This study was a pilot, open-label, randomized controlled trial approved by the institutional review board of Shanghai Changhai Hospital and registered at ClinicalTrials.gov (NCT 04389333). All of the diagnostic and therapeutic modalities were carried out in accordance with the approved guidelines.

2.3 Monitoring plan

During the clinical trial, the clinical trial inspector appointed by the bidding unit will conduct regular on-site inspection visits to the research hospital. The clinical trial supervisor is the main contact between the applicant and the researcher. The inspectors must follow the quality management standards and SOP of clinical trials of medical devices, visit the experimental units regularly or according to the actual situation for clinical supervision, urge the progress of clinical trials, check and confirm the correctness and completeness of the records and reports of all data and the input of case reports, and be consistent with the original data, so as to ensure that clinical trials are carried out in accordance with the clinical trial plan.

The specific contents of the inspectors include:

- Confirm that facilities remain acceptable.
- Ensure the implementation of the test plan by researchers during the experiment.
- Verify that all data records and reports are correct and complete and consistent with the original data.
- Research instruments should be supplied, stored, distributed and retrieved in accordance with relevant regulations, and to make corresponding records;
- The violation of the scheme and SAE should be faithfully recorded and remedied in time.
- Perform source data verification and review.
- Complete a written monitoring report after each visit.

An independent Data and safety monitoring committee (DSMC) appointed by the ethics committee, the Shanghai and National Medical Products Administration provided trial regular oversight.

2.8 Ethical issues

Before implementation of the clinical investigation, the investigator shall submit the clinical investigation plan (CIP), informed consent and other relevant documents to the medical ethics committee of the hospital where the clinical investigation will be

implemented. Only after ethical approval is obtained from the Ethics Committee, the study can get underway. Any modification to the CIP must be approved by the ethics committee before implementation. Serious adverse events (SAEs) that occur during the clinical investigation should be timely submitted to the Ethics Committee in written form.

This trial will be conducted in accordance with the protocol, Good Clinical Practice (GCP) and applicable regulatory requirements. All investigators undertaking this work have undertaken the necessary GCP training.

2.9 Benefits and risks assessment, group relatedness

In ncMCE group, patients could not only have systematic physical examination for free, but also have the possibility of FC-related symptoms improvement. The risks are that of vibration, capsule swallowing and re-interventions (surgery, endoscopy, radiology).

In placebo group, the same systematic physical examination and professional medical advice were provided throughout the study period. The risks are that of capsule swallowing and re-interventions (surgery, endoscopy, radiology).

The AEs including gastrointestinal (GI) symptoms such as abdominal pain, bloating, fever, nausea, vomiting, diarrhea; abnormal results of physical examinations and laboratory tests and capsule retention. All AEs reported spontaneously by the 107 subjects or observed by the investigator or his staff will be recorded.

Re-interventions (surgery, endoscopy, radiology) should be applied when necessary for safety consideration.

CHAPTER 3: ELIGIBILITY AND SCREENING

3.1 Study Population

This study was a pilot, open-label, randomized controlled trial approved by the institutional review board of Shanghai Changhai Hospital and registered at ClinicalTrials.gov (NCT 04389333). All of the diagnostic and therapeutic modalities were carried out in accordance with the approved guidelines. Beginning on March 26, 2020, we consecutively recruited 40 patients in Changhai Hospital using predefined inclusion criteria and exclusion criteria. After fully understanding the procedure of ncMCE and this study, patients who gave informed consent were randomly assigned into ncMCE and MCE groups (in a 1:1 ratio) by using a stratified block randomization (fixed block size four). Randomization was based on a computer-generated list of random numbers using SPSS software (version 22.0, SPSS Inc., Chicago, Illinois, United States). Only after the enrolled participants completed all baseline assessments did the endoscopist inform them about their allocation. Eligible patients were adults (≥ 18 years of age) undergoing outpatient MCE. Patients with any of the following conditions were excluded: (1) dysphagia or symptoms of gastric outlet obstruction, suspected or known intestinal stenosis, overt gastrointestinal bleeding, fistulas and strictures; (2) history of upper gastrointestinal surgery or suspected delayed gastric emptying; (3) poor general condition, asthma or claustrophobia; (4) implanted metallic devices such as pacemakers, defibrillators, artificial heart valves or joint prostheses; (5) pregnancy or mental illness; (6) current participation in another clinical study; or (7) difficulty communicating.

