
4.3 Study outcomes

4.3.1 Primary efficacy outcome

The primary endpoints were feasibility assessed by completion rate (CR) and safety evaluated by the occurrence of AE. CR was defined as complete observation of the cardia, fundus, body, angulus, antrum, and pylorus of the stomach with no technical failure. Technical failure included incomplete observation, direct contact in the ncMCE group, and examination discontinuation. The safety of ncMCE was evaluated 2 weeks after the procedure for any AEs, such as infection with SARS-CoV-2 and capsule-related AEs including abdominal pain, nausea, vomiting, and capsule impaction or retention. In the current study, the endoscopist was continuously monitored for infection until 2 weeks after the last examination.

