4.3.2 Secondary efficacy outcomes

Secondary endpoints included maneuverability score, pre-procedure perception and post-procedure satisfaction of patients, gastric examination time (GET), and diagnostic yield (DY). The maneuverability of the ncMCE system was evaluated with a questionnaire that consisted of signal transmission quality (stability and fluency), endoscopist comfort (strength needed to control joysticks and degree of fatigue), visualization of gastric mucosa (whether the mucus, foam in the stomach, and gastric fullness affected observation of gastric mucosa) and compliance of patients (patient ability to readily and correctly follow verbal instructions to change positions to assist in optimizing gastric views). The score for each index was 1 to 5, with 1 as the worst and 5 as the best, respectively, and a total ranging from 4 to 20. All patients were asked about the comfort and acceptability of the procedure using an improved pre-procedure perception and post-procedure satisfaction questionnaire, which was reviewed ease of swallowing, pain or discomfort experienced during and after the procedure, overall tolerability and convenience of the procedure, and knowledge, necessity for, and acceptability of ncMCE (Questionnaire 1) [18]. GET was defined as the time taken for gastric examination and determined using a digital stopwatch in the ESNavi software. DY or detection rate was calculated using the following formula: number of patients with positive findings divided by the total number of patients that underwent examination.

CHAPTER 5: DATA MANAGEMENT

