5.4 Data summary and report

The principal investigator writes a clinical investigation summary report in accordance to CONSORT guidelines and archives the data. Any changes to the original statistical plan should be stated and justified in the CIP and/or in the final report.

CHAPTER 6: SAFETY REPORTING AND MEDICAL MANAGEMENT

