7.5 Protocol amendments

Before clinical investigation, the CIP will be discussed and revised jointly by investigators and implementers who will sign the final copy and submit it to the ethics committee for approval before implementation.

If there is a problem with the CIP during practical implementation of the clinical investigation, a revision is necessary. The plan of revision shall be proposed to the implementer for a multi-center discussion. After then, the responsible unit will carry out revision and submit the revised CIP in a written form to the implementer and investigation units for signing. Finally, send it to the ethics committee again for approval before implementation.

If new data important related to the product for verification is found, the informed consent form must be modified and sent to the ethics committee for approval.

CHAPTER 8: STATISTICAL CONSIDERATIONS

As a pilot study to evaluate the feasibility and safety of ncMCE, the sample size was not calculated [19]. Considering the capsule endoscopy volume of Shanghai Hospital during the pandemic, we planned to recruit 40 patients into two groups. Basic characteristics were presented as means with standard deviations for continuous variables such as age, body mass index (BMI), and percentages for binary variables including sex, medical history, and symptoms. Quantitative data were summarized with parametric statistics, mean and standard deviation, or nonparametric statistics, median, and interquartile range (IQR), whereas categorical data were presented as Under the condition of normal distribution and homogeneity of variance, variance analysis was used to compare the difference in mean between groups, while a K-W test was used to compare the difference in distribution between groups and Fisher' s test was used to compare the two and disordered multi-classification data of subjects under the condition that homogeneity of variance was not satisfied. All reported Pvalues are two-sided and differences that reached $P < 0.05$ were considered statistically significant. Statistical analyses were performed with SPSS (version 22.0, SPSS Inc., Chicago, Illinois, United States).

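### Allocation is called stratified but no stratification factor is named, and Chapter 8 compares the arms without strata: a small, conditional loss of precision on continuous secondary endpoints

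*Combined protocol and SAP*

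**What the plan says.** Section 3.1 describes 1:1 allocation to ncMCE or MCE "by using a stratified block randomization (fixed block size four"), from a list generated in SPSS. It gives no factor, no levels and no number of strata. The same section states that "we consecutively recruited 40 patients in Changhai Hospital using predefined inclusion criteria and exclusion criteria", and section 5.2 says that one endoscopist performed every examination.

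Chapter 8 sets out the comparisons. Under normality and equal variances, "variance analysis was used to compare the difference in mean between groups"; otherwise "a K-W test was used to compare the difference in distribution between groups", with Fisher's test for categorical data. None of these has a stratum term or a stratified form, and no reason is given for leaving strata out. P values are two-sided at 0.05; no confidence intervals are specified.

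On endpoints, section 4.3.1 states: "The primary endpoints were feasibility assessed by completion rate (CR) and safety evaluated by the occurrence of AE". Section 4.3.2 states: "Secondary endpoints included maneuverability score, pre-procedure perception and post-procedure satisfaction of patients, gastric examination time (GET), and diagnostic yield (DY"). On size, Chapter 8 says: "As a pilot study to evaluate the feasibility and safety of ncMCE, the sample size was not calculated".

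**The concern.** Blocking within strata balances the arms on the stratification factor, so differences between strata largely drop out of the arm difference. A test that ignores the strata still counts those differences as error. Its standard error is then too large for the design, its P values are too big, and any interval built from it is too wide. With 40 patients, a number set by procedure volume, efficient analysis is one of the few ways to gain precision.

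The wording also leaves two possibilities that call for different corrections. Either a patient-level factor was used and is missing from both the description and the analysis, or there was one list and 'stratified' is simply the wrong word.

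**Working it through.** **1. Can the factor be inferred?** The two usual defaults are excluded. Recruitment was at one hospital (3.1) and one operator did all examinations (5.2), so neither centre nor operator can define strata. Only a patient-level factor or a single list remains, and the text does not say which.

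**2. Inputs.** From the documents: N = 40, 1:1, blocks of four, two-sided 0.05. A single list gives 40/4 = 10 complete blocks and 20 per arm. The plan states no power, effect size or SD, so there is no figure of its own to reproduce. Assumed here: total within-arm SD of 1, S equally likely strata, and a share R² of outcome variance explained by the strata.

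**3. Width of the 95% interval for the arm difference.**
- Without a stratum term: half-width = t(38) × √(2/20) = 2.024 × 0.316 = 0.64 SD.
- With a stratum term: residual variance falls to 1 − R² and the degrees of freedom to 39 − S. The ratio of widths is approximately √(1 − R²) × t(39 − S)/t(38), with t(37) = 2.026 and t(35) = 2.030.

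| Assumed R² | √(1 − R²) | Ratio, S = 2 | Ratio, S = 4 | Narrowing by simulation, S = 2 to 4 |
|---|---|---|---|---|
| 0 | 1.000 | 1.001 | 1.003 | none (0.1-0.6% wider) |
| 2% | 0.990 | 0.991 | 0.993 | 0.4-0.9% |
| 5% | 0.975 | 0.976 | 0.977 | 2.0-2.4% |
| 10% | 0.949 | 0.950 | 0.951 | about 5% |
| 30% | 0.837 | 0.837 | 0.839 | 16-17% |

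The simulations used blocks of four within strata and allowed unfinished blocks. Eight strata that explain nothing cost 2.6% in width.

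**4. Direction of the error.** The true variance of the arm difference under stratified blocks is about (1 − R²) times what the unstratified test assumes. Its cut-off of 2.024 therefore acts like 2.024/√(1 − R²).
- R² = 10%: 2.024/0.949 = 2.13, a true size of about 0.039 (simulated 0.038-0.041).
- R² = 30%: 2.024/0.837 = 2.42, a true size of about 0.020 (simulated 0.020-0.022).

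Both are below 0.05. With the stratum term, simulated size is 0.048-0.052.

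**5. Power, for illustration only.** For a 0.9 SD difference (an assumption) and two strata, power rises from 0.799 to 0.827 at R² = 10% and from 0.829 to 0.911 at 30%. A separate run gave 0.804 to 0.831 at 10%. At 2% the change is at most about half a percentage point.

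**6. Rank fallback.** At 0.9 SD, Kruskal-Wallis against a linear model on ranks with arm and stratum:
- S = 2: 0.777 against 0.808 (R² = 10%), 0.789 against 0.892 (30%).
- S = 4: 0.776 against 0.800 (10%), 0.791 against 0.885 (30%).

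The van Elteren test gave 0.799 and 0.887 with two strata, and 0.767 and 0.867 with four. The rank model did at least as well in each case, so one rule is enough. Its simulated size was 0.047-0.055.

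**7. Primary endpoints.** If completion is near 100% and adverse events are rare (an assumption), strata have little variation to explain. Fisher's test at 20 against 20 gives P = 0.106 for 0 against 4 failures and P = 0.047 for 0 against 5. Sparse counts, not unmodelled strata, limit that comparison.

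**The case against.** The strongest reply is that nothing certain is wrong beyond one undefined word. The documents do not show which branch is true. Some of their wording does not fit this trial: section 2.9 refers to a placebo arm and to 107 subjects, and section 7.5 to a multi-centre discussion, in a 40-patient, one-hospital comparison of two systems. A loose use of 'stratified' is therefore quite possible, and in that case the statistical loss is nil. Even if strata existed, a weak factor would make the gain negligible. Nor does the plan specify the intervals whose width is computed above. All of this stands and keeps the severity low. It does not remove the need to settle the point, because one of the two corrections applies whichever branch is true.

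It is also fair that the gain does not extend equally to every score. Of the four maneuverability domains, signal transmission and endoscopist comfort are features of the system or operator, which a patient-level stratum is unlikely to explain. Questionnaire 2 also anchors the joystick-strength item at 5 for MCE. Little gain should be expected there.

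A reader might infer more than the documents support:
- **That ignoring strata produces false positives.** The error runs the other way (step 4).
- **That the completion and safety conclusions are undermined.** They are hardly affected (step 7).
- **That fixed blocks of four in an open-label trial let someone foresee allocations.** Nothing shows that the endoscopist enrols patients or sees the list. Recruitment was consecutive, consent came before randomisation, and a blinded researcher judges completion.

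**Conclusion.** The point holds as a low-severity gap in description and efficiency. The text supplied for review names no stratification factor and the analysis uses none. Some sections were not available (numbering passes from 2.3 to 2.8 and from 7.1 to 7.3), so a factor could be named there.

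If 2 to 4 strata were used, adjustment would narrow the interval for gastric examination time or satisfaction by about 0.5-1% (2% of variance explained), 2-2.5% (5%), 5% (10%) or 16% (30%). With a single list the gain is zero. The R² values are assumptions; the documents give no basis for choosing among them.

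**What to change.** Check the randomisation list, then follow one branch.

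- **Single list:** delete 'stratified' from section 3.1. Chapter 8 stays as it is.
- **Strata used:** name the factor or factors and levels in section 3.1. Add stratum as randomised to the linear model for gastric examination time and the questionnaire scores, and make this the governing analysis. Where the rank fallback applies, rank all 40 values and fit the same arm + stratum model to the ranks, whatever the number of strata. Keep Fisher's test for binary outcomes. It would also help to report the arm difference with a 95% interval, which Chapter 8 does not currently ask for.

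Either way, section 5.4 governs how to record the change: "Any changes to the original statistical plan should be stated and justified in the CIP and/or in the final report". If unstratified results already exist, show both and say that the stratified analysis governs.

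The cost is one model term and a few sentences, with no extra patients, visits or data beyond the stratum on the list. If 2 to 4 strata explain nothing, intervals widen by about 0.5%; with many small strata, somewhat more.

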5.2 Data collection

Information on the basic characteristics of the enrolled patients was collected prospectively. Each patient was followed up for 2 weeks by telephone and hospital information system to confirm capsule excretion and any adverse events (AEs), including COVID-19 infection. The maneuverability questionnaire for the endoscopist and improved questionnaire on pre-procedure perception and post-procedure satisfaction for patients were completed after the examination. To avoid systematic bias, a single endoscopist ([name]) performed each examination and made the diagnoses for all enrolled patients immediately. The evaluation of completion was made by another blinded researcher ([name]).

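### Fixed blocks of four with no described concealment step make about 25% to 33% of allocations foreseeable to anyone at enrolment who knows the block size and the past allocations

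*Combined protocol and SAP*

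**What the plan says.** Section 3.1 sets out the design: "This study was a pilot, open-label, randomized controlled trial". It reports that "we consecutively recruited 40 patients in Changhai Hospital". Patients who consented were "randomly assigned into ncMCE and MCE groups (in a 1:1 ratio", and this was done "by using a stratified block randomization (fixed block size four". The list was computer-generated in SPSS. Randomisation is called stratified, but no stratification factor is named.

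On disclosure, Section 3.1 says: "Only after the enrolled participants completed all baseline assessments did the endoscopist inform them about their allocation". Section 5.2 says that a single endoscopist "performed each examination and made the diagnoses for all enrolled patients immediately". Chapter 8 says that "the sample size was not calculated"; the total of 40 rests on capsule endoscopy volume.

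Sections 3.1, 3.2.2, 5.2 and 5.3 are where one would look for the rest of the allocation procedure. They do not say who held the list, who decided eligibility, or how the next allocation was hidden until a patient was committed. Section 3.2.2 gives consent to the investigator without saying whether that is the endoscopist.

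The plan does state some safeguards: consecutive recruitment, predefined criteria, consent before assignment, disclosure to patients only after baseline assessments, and a separate blinded researcher who judges completion (Section 5.2).

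**The concern.** In a block of four at 1:1, the fourth allocation is always fixed by the first three, and the third is fixed whenever the first two match. The block size is printed in the protocol. In an open-label trial with one operator, past allocations are visible at least to that operator. A person who knows both can often tell which arm comes next.

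This matters when entry depends on judgement. The exclusions in Section 3.1 include trouble communicating, poor general health and suspected slow gastric emptying. Communication bears on the outcomes: under Section 4.2 the ncMCE patient is directed through the audio-visual link, under Section 4.3.1 direct contact in that arm counts as a technical failure, and under Section 4.3.2 compliance with verbal instructions forms part of the maneuverability score. If borderline patients were deferred or excluded according to the next slot, the arms would differ before any examination began. With 20 patients per arm, each patient is 1/20 = 5 percentage points of the completion rate. Chapter 8 plans between-group tests at a two-sided 0.05 level, so comparability of the arms matters even in a pilot.

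**Working it through.** The plan gives no predictability figure to reproduce.

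**Inputs.** Block size 4 fixed, ratio 1:1, 40 patients, one hospital (all Section 3.1). The number of strata is not given, so 1 to 8 equal strata are assumed. An allocation counts as certain when one arm is already used up within the block.

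**Certain allocations, complete blocks.** There are six equally likely 2:2 sequences.
- Two (AABB, BBAA) make positions 3 and 4 certain.
- Four make only position 4 certain.
- Expected number per block: (2 × 2 + 4 × 1)/6 = 8/6 = 4/3, or 33.3%. By position: 0, 0, 1/3, 1.
- 40/4 = 10 blocks, so 10 × 4/3 = 13.3 of 40. The possible range is 10 to 20.

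**Effect of strata.** Strata leave some blocks incomplete, and the late positions are the predictable ones. Simulation of 40 patients (20,000 runs) gives:

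| Assumed equal strata | Share certain |
|---|---|
| 1 | 33.3% |
| 2 | 31.2% |
| 4 | 29.1% |
| 8 | 25.0% |

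One third is therefore the upper end of the range.

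**Guessing the arm that is behind.** For a permuted sequence of m + m, the expected number of correct guesses is m + (2^(2m)/C(2m, m) − 1)/2.
- Block of four (m = 2): 2 + (16/6 − 1)/2 = 2.833 of 4 = 70.8%, or 28.3 of 40. By position: 1/2, 2/3, 2/3, 1.
- Simple randomisation: 50%.

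**Alternatives.** The expected number of certain allocations in a permuted sequence of m + m is 2m/(m + 1).

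| Scheme | Certain in advance | Best guess correct |
|---|---|---|
| Fixed 4 (the plan) | 33.3% (13.3 of 40) | 70.8% |
| Random 4/6 | about 5.7% | about 69% |
| One 20:20 list | 40/21 = 1.9 of 40 | 20 + (2^40/C(40,20) − 1)/2 = 23.5 of 40 = 58.7% |

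The 4/6 figures come from simulation (3,000 runs) with an observer who knows the two possible sizes but not the ones drawn. Varying the block size removes most of the certainty and very little of the guessability.

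**The case against.** The strongest reply is that the link between predictability and enrolment is not in the documents. Selective entry needs the person who judges eligibility to know the block size and the earlier allocations. Section 3.1 says only that the endoscopist told patients their allocation, and Section 5.2 gives that person the examinations and diagnoses. A reader might infer that the endoscopist enrolled patients, saw the future list, or steered patients between arms. The text supports none of these. What the endoscopist necessarily knows is past allocations, after the fact. This part of the objection stands, and every figure above is conditional on it.

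A second reply is that recruitment was consecutive and completion was judged blind. Consecutive recruitment does work against deferral, but it operates through the same judgement-based criteria, so it reduces the risk without removing it. The blinded assessor limits detection bias on completion and does nothing about who enters. Delaying disclosure until after baseline keeps the allocation from the patient, not from staff.

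Two further inferences should be resisted. One is that disclosure by the endoscopist breaches the non-contact design: the plan does not say that disclosure was in person, and Section 4.2 describes separate routes and an audio-visual link. The other is that the baseline table could not reveal steering: Chapter 8 gives its baseline variables as examples, so the list may not be complete.

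Pilot status and the lack of a sample size calculation do not answer the point, since it concerns comparability of the arms and not power.

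**Conclusion.** The point holds as a conditional risk. The plan states a predictable scheme in a setting where past allocations are visible, and describes no step that hides the next one. If the person judging eligibility knows the block size and the past allocations in the stratum, about 25% to 33% of allocations are certain in advance, over 1 to 8 assumed equal strata. The best guess is right 70.8% of the time in complete blocks. That the enrolling person knew the block size is an assumption, made plausible by its being printed in the protocol.

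The central gap is the undescribed concealment; the fixed block size makes it worse. The documents give no evidence that selective enrolment happened. The point should be dealt with, but it does not by itself invalidate the trial.

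**What to change.** In Section 3.1:

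1. **Concealment first.** Have existing staff who neither screen nor examine, for example the data manager, hold the list and release each allocation only after eligibility and consent are logged. State who decides eligibility.
2. **Name the stratification factors, or say that there are none.** The choice of list depends on this.
3. **Replace the fixed blocks.** If unstratified, use one permuted 20:20 list. Otherwise use randomly varying block sizes that are not disclosed to the endoscopist or to enrolling staff. Because guessing stays near 69% with varying 4/6 blocks, this does not replace step 1.

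The cost is a new computer-generated list and a sentence or two, with slightly looser balance of the arms over calendar time.

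Section 3.1 describes recruitment in the past tense. If enrolment is complete, state who held the list, who enrolled, whether they knew the block size, and how the next allocation was concealed. Use the screening form and enrolment log listed in Section 7.1 to report screened patients excluded, by reason and by position in the block. State the limitation in the report.
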